### **(5). Annualized rate of moderate or severe COPD exacerbation after the index date**

The definition of moderate or severe COPD exacerbation:

- a. Moderate exacerbations will be defined as an outpatient visit with a diagnosis code for COPD in any field + a prescription for an oral corticosteroid or an antibiotic for respiratory infections, prescriptions within 30 days of each other were considered as continuation of the initial exacerbation.
- b. Severe exacerbations will be defined as a hospitalization or emergency room visit with a primary diagnosis for COPD; hospitalizations or emergency room visits within 30 days of each other were considered as continuation of the initial exacerbation.

For annualized rates, it will be calculated for each cohort as follows:

Annualized rate among the Tio+Olo cohort = (total number of events in the Tio+Olo cohort during the given time period) / (total person-year at risk from current use of Tio+Olo during the given period)

Annualized rate among the comparison cohort = (total number of events in the comparator LABA/ICS cohort during the given time period) / (total person-year at risk from current use of comparator LABA/ICS during the given period)

For annualized rate of moderate or severe COPD exacerbations, the rate ratio of Tio+Olo – exposed group relative to LABA/ICS group, along with 95% CI will be derived using negative binomial model.

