Naïve to COPD treatment, or at least one dispensing of the following categories of medications either alone or in combination: 1) SABA or SAMA or SABA+SAMA, 2) LAMA or LABA monotherapy, 3) theophylline or mucolytics, in the 12 months before the index date;

- Moderate:  
At least one dispensing of LAMA + LABA in the 12 months before the index date;
- Severe:  
Occurrence of at least one of the following events in the 12 months before the index date:
  - Hospitalization with a primary diagnosis for COPD
  - Hospitalization with a primary diagnosis for pneumonia
  - Second course of antibiotics for respiratory tract infections; a single course of antibiotic treatment involving multiple dispensings is defined as that involving consecutive dispensings of antibiotics with fewer than 7 days between the end of days of supply of one dispensing and the date of the next dispensing
  - Second course of systemic corticosteroids for the treatment of COPD exacerbation; a single course of systemic corticosteroids involving multiple dispensings is defined as that involving consecutive dispensings with fewer than 7 days between the end of days of supply of one dispensing and the date of the next dispensing.
  - Two diagnoses of COPD exacerbation (ICD-10: J44.1; ICD-9: 491.21) without hospitalisation
- Very severe:  
Occurrence of at least one of the following events in the 12 months before the index date unless other time period is specified:
  - Dispensed oxygen therapy
  - Dispensed nebuliser therapy

Diagnosis codes and drug codes are listed in the annex.

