## Appendix 1. SAS code template for negative binomial model in the analysis of the secondary outcomes of interest

The following codes are provided by Boehringer Ingelheim statistician

```
PROC GENMOD DATA=test;
CLASS treat (ref='LABA/ICS') cova_cat;
MODEL ep_count = treat cova_cat cova_con /
DIST=negbin LINK=LOGTYPE3 OFFSET=logt;
LSMEANS treat / DIFF CL;
ESTIMATE 'Treatment effect on ratio-scale' treat 1 -1 / EXP;
RUN;
```

(In the model,  
treat: Tio+Olo group OR LABA/ICS group;  
Cova\_cat: categorical covariates;  
Cova\_con: continuous covariates)

For univariate analysis, Cova\_cat and Cova\_con are not applicable.

For calculating incidence rate ratio with 95% CI of triple therapy initiation (Tio+Olo vs. LABA/ICS),  
ep\_count (response): 1 (triple therapy initiation occurred per patient) or 0 (triple therapy initiation not occurred per patient);  
logt: nature log of the time at risk (first event per patient)

For calculating ratio (with 95% CI) of annualized rate of moderate or severe COPD exacerbations and annualized rate of prescriptions of rescue medications (Tio+Olo vs. LABA/ICS),  
ep\_count (response): number of events per patient  
logt: nature log of the time at risk per patient

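### The moderate-exacerbation count ignores days of supply, so near-continuous treatment refilled every 31 to 34 days can count as 11 to 12 exacerbations a year

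*SAP*

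**What the plan says.** SAP 7.2.2 (5) defines a moderate exacerbation as "an outpatient visit with a diagnosis code for COPD in any field + a prescription for an oral corticosteroid" or a respiratory antibiotic, and separates one event from the next with the rule "prescriptions within 30 days of each other were considered as continuation of the initial exacerbation". It does not say whether the 30 days run from the previous prescription or from the first one of the episode, and it does not mention days of supply. SAP 7.3 uses the same wording for the baseline exacerbation history, categorized 0, 1 or 2+, which enters the propensity score under SAP 10.1. Severe events have their own rule, based on encounters: "hospitalizations or emergency room visits within 30 days of each other were considered as continuation of the initial exacerbation".

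The severity definition in SAP 7.3 treats the same drug classes differently. One criterion for the Severe level is "Second course of systemic corticosteroids for the treatment of COPD exacerbation", with a parallel criterion for antibiotics. There, several dispensings form a single course when there are "fewer than 7 days between the end of days of supply of one dispensing and the date of the next dispensing".

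SAP Appendix 1 puts the count into a negative binomial model: "ep\_count (response): number of events per patient", with log time at risk as the offset.

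**The concern.** A patient kept on oral corticosteroid or antibiotic treatment through repeated long supplies is receiving treatment that the SAP itself would call one course. Under the 30-day rule, the number of exacerbations recorded for that patient depends on whether the refill falls just before or just after day 30. A few such patients, each contributing about a dozen events a year, carry heavy weight in a count model where the other patients contribute about one.

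If these events do not respond to the index drug and occur equally in both arms, they dilute the rate ratio toward 1 and add overdispersion. In the baseline history, the same patient moves from the 1 category to 2+ on refill timing alone, and that category feeds the matching.

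**Working it through.** The documents give no figure for this rule, so there is none to reproduce. The check has two parts.

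**1. Counting episodes**

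Inputs from the SAP: the 30-day rule (7.2.2 (5)) and the course rule of under 7 days from end of supply (7.3). Assumed: 365 days at risk, prescriptions on days 0, k, 2k and so on, 28-day supplies, and a COPD-coded outpatient visit at every refill.

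The number of prescriptions is floor(364/k) + 1. Chained: a new episode starts if the gap from the previous prescription exceeds 30 days. Anchored: a new episode starts if a prescription falls more than 30 days after the first of the episode. Course rule: a new course starts if k − 28 is 7 or more.

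| Refill interval k (days) | Prescriptions | Chained | Anchored | Course rule |
|---|---|---|---|---|
| 28 | 14 | 1 | 7 | 1 |
| 30 | 13 | 1 | 7 | 1 |
| 31 | 12 | 12 | 12 | 1 |
| 33 | 12 | 12 | 12 | 1 |
| 34 | 11 | 11 | 11 | 1 |
| 35 | 11 | 11 | 11 | 11 |

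- At 31 to 34 days the result is 11 to 12 on both date-to-date readings, against one course (off-supply gaps of 31 − 28 = 3 to 34 − 28 = 6 days).
- At 28 to 30 days the result is 1 or 7, depending on an anchor that the SAP does not state.
- At 35 days with 28-day supplies the gap is 7 days, so both rules split and there is no conflict.
- If the 30 days ran from end of supply, every row would be 1. The sentence measures between prescriptions, so that is not its natural reading.
- The rules also differ in the other direction: 7-day supplies every 20 days are 1 exacerbation chained (10 anchored) but 19 courses.

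**2. Size of the dilution**

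Background rate: protocol 9.5 assumes that 25% of ICS/LABA patients have a first event by 103 days. With a constant hazard this is −ln(0.75)/103 × 365 = 1.02 per year, used here as the comparator event rate. Affected patients are assumed to refill every 31 to 34 days, on average 32.5, which is 365/32.5 = 11.23 events a year. For a share s of affected patients in each arm, the added rate is a = 11.23 × s, and the diluted ratio is (R × 1.02 + a)/(1.02 + a), where R is the true ratio.

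| Share s (assumed) | Added rate a | True 0.85 becomes | True 0.90 becomes |
|---|---|---|---|
| 0.1% | 0.011 | 0.878/1.031 = 0.852 | 0.929/1.031 = 0.901 |
| 1% | 0.112 | 0.979/1.132 = 0.865 | 1.030/1.132 = 0.910 |
| 2% | 0.225 | 1.092/1.245 = 0.877 | 1.143/1.245 = 0.918 |
| 5% | 0.562 | 1.429/1.582 = 0.903 | 1.480/1.582 = 0.936 |

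**The case against.** **Different constructs.** The course rule defines a treatment course for one level of a baseline covariate. The 30-day rule defines an exacerbation episode. The severity definition lists second courses and diagnosed exacerbations as separate criteria, so the SAP does not equate them, and where the construct is the same (baseline and outcome exacerbations) the wording is the same. This stands. A reader might infer that the SAP contradicts itself. The documents support only that it uses inconsistent conventions for related quantities from the same drug classes.

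**Conditions on the over-count.** A refill without a COPD-coded outpatient visit is not an event, and the documents do not say how often refills come with one. If half the intervals were 30 days or less, the added rate would roughly halve under the chained reading. Both points stand and make the figures above upper illustrations for each share. A COPD code in any diagnosis field is, however, an easy condition to meet in a cohort selected for COPD.

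**No difference between arms.** The rule is identical in both arms, and matching on the baseline history may help balance such patients. This also stands. A reader might infer that one treatment is favoured, but that would need different maintenance steroid or antibiotic use after matching, and the documents give no such figures. Dilution toward 1 needs no difference between arms.

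**Power.** It is tempting to quote a loss of power. That depends on the dispersion and the on-treatment time, neither of which the documents give, so none is claimed.

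**Conclusion.** The concern holds in limited form. The 30-day prescription rule can turn near-continuous treatment with 28-day supplies into 11 to 12 moderate exacerbations a year when refills fall 31 to 34 days apart at COPD-coded visits. The same sentence gives 1 or 7 for refills at 28 to 30 days, depending on an unstated anchor. That ambiguity alone could lead the second analyst foreseen in protocol 9.8 to a different count.

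The reach is narrow: the moderate and all-exacerbation rows of SAP Table 6, and the baseline 0/1/2+ history. A reader might infer that the primary result is at risk. It is not, because time to first event does not use the merging rule. Severe events are separated by encounters, and no defect is shown in that rule.

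The size is unknown, because it depends on the share of such patients. It is negligible at 0.1% (0.85 becomes 0.852) and material at 5% (0.85 becomes 0.90). These figures assume events that are unrelated to the index drug and equally common in both arms, a background rate of 1.02 per year, and a qualifying visit at every refill. The change is worth making because it is cheap, not because a large bias has been shown.

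**What to change.** In SAP 7.2.2 (5) and in the baseline exacerbation history in 7.3:

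- Keep the 30-day rule and state that it runs from the previous qualifying prescription.
- Add that an oral corticosteroid or antibiotic dispensing is also a continuation if it starts fewer than 7 days after the end of supply of the previous one.
- Apply the same rule to outcome and baseline counts. Leave the rule for hospitalizations and emergency room visits as it is.

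The addition can only merge events, never split them, so short supplies 20 days apart remain one episode. It acts only where the gap is at least 31 days and the time off supply at most 6 days, which requires at least 31 − 6 = 25 days of supply. It therefore mainly removes maintenance refills. Refills of 28-day supplies at 35 days would still count separately.

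The cost is a sentence or two in each of two sections and a small programming change; the severity definition already needs days of supply. The downside is that a genuine new moderate exacerbation during continuous treatment would not be counted separately. One that leads to a hospitalization or emergency room visit would still count as severe.

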### 7.3 COVARIATES

Demographic characteristics and cohort entry information:

- Sex
- Age
- Calendar year of cohort entry
- Season of index date (winter, Dec-Feb; spring, Mar-May; summer, Jun-Aug; fall, Sep-Nov )

Additional characteristics will be defined during the 1-year pre-index baseline period:

- Previous COPD treatments
  - LAMA monotherapy
  - LABA monotherapy
  - ICS monotherapy
  - LAMA/ICS free combination therapy
- Use of other respiratory drugs
  - Mucolytics
  - Theophylline
  - Short-acting beta-agonists
  - Short-acting muscarinic antagonists
- Previous acute COPD exacerbation (measured both 12 months and in the 30 days prior to cohort entry), categorized as 0, 1, or 2+.
  - All exacerbations (Moderate+Severe)
  - An outpatient visit with a diagnosis code for COPD in any field + a prescription for an oral corticosteroid or an antibiotic for respiratory infections (Moderate); prescriptions within 30 days of each other were considered as continuation of the initial exacerbation.
  - Hospitalizations or emergency room visits with a primary diagnosis for COPD

(Severe); hospitalizations or emergency room visits within 30 days of each other were considered as continuation of the initial exacerbation.

- Hospitalizations caused by exacerbation of heart failure in 12 months prior to index date, categorized as
  - 0;
  - 1;
  - 2+.
- All-cause hospitalizations in 12 months prior to index date;
  - 0;
  - 1;
  - 2+.
- Comorbidities:
  - Cardiovascular disease
  - Cerebrovascular disease
  - Diabetes
  - Chronic kidney disease
  - Pneumonia
  - Cancer
  - Cirrhosis
- Charlson Comorbidity Index (CCI)
- History of medications dispensed in the 12 months before or on the index date will be identified from the pharmacy dispensing history:
  - Cardiovascular drugs:
    - antihypertensives;
    - antiarrhythmics;
    - nitrates;
    - heart failure medications
  - Lipid-lowering medications
  - Blood glucose-lowering medications
  - Anticoagulants and antiplatelet agents
  - Antibiotics
  - Antineoplastic agents
- COPD severity

The definition of the severity of COPD in this study was developed based on the information in previous studies, GOLD recommendations and clinical practice in Taiwan, see below. Patients who fulfil criteria for more than one category will be classified as being in the most severe category.

Operational definition of COPD severity:

- Mild:

Naïve to COPD treatment, or at least one dispensing of the following categories of medications either alone or in combination: 1) SABA or SAMA or SABA+SAMA, 2) LAMA or LABA monotherapy, 3) theophylline or mucolytics, in the 12 months before the index date;

- Moderate:  
At least one dispensing of LAMA + LABA in the 12 months before the index date;
- Severe:  
Occurrence of at least one of the following events in the 12 months before the index date:
  - Hospitalization with a primary diagnosis for COPD
  - Hospitalization with a primary diagnosis for pneumonia
  - Second course of antibiotics for respiratory tract infections; a single course of antibiotic treatment involving multiple dispensings is defined as that involving consecutive dispensings of antibiotics with fewer than 7 days between the end of days of supply of one dispensing and the date of the next dispensing
  - Second course of systemic corticosteroids for the treatment of COPD exacerbation; a single course of systemic corticosteroids involving multiple dispensings is defined as that involving consecutive dispensings with fewer than 7 days between the end of days of supply of one dispensing and the date of the next dispensing.
  - Two diagnoses of COPD exacerbation (ICD-10: J44.1; ICD-9: 491.21) without hospitalisation
- Very severe:  
Occurrence of at least one of the following events in the 12 months before the index date unless other time period is specified:
  - Dispensed oxygen therapy
  - Dispensed nebuliser therapy

Diagnosis codes and drug codes are listed in the annex.

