## **6.3 STUDY POPULATION**

### **Inclusion Criteria:**

1. At least one prescription for Tio/Olo combined inhaler or a LABA/ICS combined inhaler between 1st January 2014 and 31st December 2019.
  - a) The first dispensing of either Tio/Olo or LABA/ICS combined inhaler will be defined as the index date;
  - b) For the main analyses, only fixed dose combination (FDC) inhalers will be included.
2. Aged  $\geq$  40 years on the index date
3. At least one diagnosis of COPD (ICD9: 491.x, 492.x, 496; ICD10: J41.x, J42, J43.x, J44.x) at any time prior to or on the index date;

[figure not shown]
4. At least one year of continuous medical and health insurance plan prior to the index date will be required to allow for a look-back period for the covariates and identification of new use of the study drugs;
5. At least one record in the health insurance system database.

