### **7.2 OUTCOMES**

#### **7.2.1 Primary outcomes**

##### **➤ Time to the first moderate or severe COPD exacerbations after index date**

The definition of moderate or severe COPD exacerbation:

- a. Moderate exacerbations will be defined as an outpatient visit with a diagnosis code for COPD in any field + a prescription for an oral corticosteroid or an antibiotic for respiratory infections
- b. Severe exacerbations will be defined as a hospitalization or emergency room visit with a primary diagnosis for COPD

Detailed diagnosis codes are listed in Annex.

Tio/Olo users will be matched to the comparator through 1:1 propensity score matching. For the analysis of the primary outcome, individuals will be followed up from the index date until the first moderate or severe COPD exacerbation. For detailed, please refer to section [10.1](#). As time-to-event data, the main analysis will be univariate proportional hazard regression analysis to estimate the hazard ratio (Tio/Olo vs. comparator) and its 95% confidence interval (CI). Detailed analytic approach is described in Section [10.1](#).

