**Comorbidities:**

Cardiovascular disease  
 Cerebrovascular disease  
 Diabetes  
 Chronic kidney disease  
 Pneumonia  
 Cancer  
 Cirrhosis

**Charlson Comorbidity Index  
(CCI)**

History of medications dispensed in 1 year prior to index date

Cardiovascular drugs:  
 Antihypertensives  
 Antiarrhythmics  
 Nitrates  
 Heart failure medications  
 Lipid-lowering medications  
 Blood glucose-lowering medications  
 Anticoagulants and antiplatelet agents  
 Antibiotics  
 Antineoplastic agents

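### A COPD exacerbation treated on the day the study inhaler starts is only partly captured by the propensity score, because the exacerbation, hospitalization and severity windows are worded to end before the index date

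*SAP*

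**What the plan says.** Time zero is a dispensing date: "The first dispensing of either Tio/Olo or LABA/ICS combined inhaler will be defined as the index date" (SAP 6.3).

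SAP 7.3 sets the clinical covariates under one lead-in, "Additional characteristics will be defined during the 1-year pre-index baseline period". Within it:

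- Exacerbation history: "Previous acute COPD exacerbation (measured both 12 months and in the 30 days prior to cohort entry), categorized as 0, 1, or 2" (or more).
- COPD severity, for the severe and very severe categories: "Occurrence of at least one of the following events in the 12 months before the index date".
- Hospitalization counts: the 12 months prior to the index date.
- Medication history: "History of medications dispensed in the 12 months before or on the index date will be identified from the pharmacy dispensing history". The list includes antibiotics but not systemic corticosteroids.

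The Table 1 shell in SAP Annex 1 labels the last item "History of medications dispensed in 1 year prior to index date", without the index day. Protocol 9.3.3 uses the same windows as SAP 7.3. The COPD diagnosis needed for eligibility may fall before or on the index date.

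SAP 10.1 puts every covariate except season into the score. It adds a covariate to the outcome model only if its absolute standardized difference exceeds 0.1 after matching. The primary outcome is "Time to the first moderate or severe COPD exacerbations after index date" (SAP 7.2.1), while SAP 10.1 starts follow-up from the index date itself.

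**The concern.** Consider a patient seen for worsening COPD who leaves with a first study inhaler and a course of oral corticosteroid, both dispensed that day. This meets the plan's definition of a moderate exacerbation. As the windows are worded, it is in neither exacerbation count and does not contribute to severity. By the outcome's title it is not an outcome either.

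Being in an exacerbation at initiation plausibly affects both the choice of inhaler and the risk of an early recurrence. The protocol's background (section 7) reports that the guideline ties ICS/LABA initiation to frequent exacerbations and high eosinophils. If such visits are more common among ICS/LABA initiators after matching, the hazard ratio moves in favour of Tio/Olo with no drug effect behind it.

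The plan could not see this. Table 1 uses the same windows as the score, and the outcome model can adjust only for covariates that have been built. Protocol 9.9 accepts that lung function and COPD duration may be unavailable as confounders. This one is in the claims.

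**Working it through.** **Step 1. What each item records about an index-day episode, as worded**

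| Item in the score | Window | Index-day episode recorded? |
|---|---|---|
| Exacerbations, 30 days and 12 months | prior to cohort entry | No |
| Hospitalizations | prior to the index date | No |
| COPD severity | before the index date | No |
| Antibiotics (medication history) | before or on the index date (7.3); prior to it (Table 1) | Indirectly, if an antibiotic was given |
| Systemic corticosteroids | not in the medication list | No |

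The antibiotics item is a weak stand-in. It spans a year, is not tied to a COPD visit, and in SAP Appendix 5 includes antimycotics and antimycobacterials. As a yes/no item, it does not change for a patient who already had any such drug in the preceding year.

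**Step 2. What the score does hold.** Episodes dated in the 30 days or 12 months before the first dispensing are included, among them an emergency visit or admission shortly beforehand. The gap is the index day.

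**Step 3. Possible size.** The plan gives no figure to reproduce. For a binary factor left unbalanced, with share p_T among Tio/Olo and p_I among ICS/LABA initiators and later hazard multiplied by R, the hazard ratio at time zero is multiplied by

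B = (1 + p_T(R − 1)) / (1 + p_I(R − 1)).

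The shares and R are assumptions; none is in the documents.

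| p_I | p_T | R | B |
|---|---|---|---|
| 0.15 | 0.10 | 1.5 | 1.050/1.075 = 0.977 |
| 0.20 | 0.10 | 1.5 | 1.050/1.100 = 0.955 |
| 0.20 | 0.10 | 2 | 1.100/1.200 = 0.917 |
| 0.25 | 0.10 | 2 | 1.100/1.250 = 0.880 |
| 0.20 | 0.20 | 2 | 1.200/1.200 = 1.000 |

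**Step 4. What reduces it**, taking the 20% versus 10%, R = 2 case:

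- If the antibiotics item removed half of the episodes from the imbalance, B = (1 + 0.05)/(1 + 0.10) = 0.955.
- B applies at time zero. A Cox model averages over follow-up, and patients with the raised hazard leave the risk set sooner. I took the planning rate for patients without an index-day episode (25% with an event by 103 days, so a daily hazard of −ln(0.75)/103 = 0.00279), no true drug effect and no censoring. The large-sample Cox hazard ratio is then 0.935 over one year and 0.949 over six.
- If the doubled hazard lasts only 90 days (assumed), it is 0.980 over six years.

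For scale, Protocol 9.5 plans on a hazard ratio of 0.90.

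**The case against.** Four arguments weigh against the point.

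**The score is not blind to the index visit.** A reader might infer that the index-visit exacerbation is absent from the score and wholly unadjusted. The documents do not support that. Index-day antibiotics enter under SAP 7.3, and recent exacerbation history enters in full. This stands: the capture is partial, not nil.

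**Exclusion of the index day is inferred.** No sentence states it. It follows from wording that names the index day for some items and not for others. One of those contrasts is an eligibility criterion, and Table 1 drops the index day for the very item that includes it in 7.3, so the wording may simply be loose. This also stands, but it is itself a reason to state the rule.

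**Ending baseline before time zero is a defensible convention, and moving every window would do harm.** SAP 7.3 defines moderate severity by a dispensing of LAMA plus LABA. Tio/Olo is listed as a LABA/LAMA in Appendix 3 and is dispensed on the index date by definition. With that day in the severity window, every Tio/Olo initiator could become at least moderate, and the covariate would partly encode treatment. This stands in full against a blanket extension, but not against a separate exacerbation indicator.

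**The size is assumed and runs one way.** The same background section says ICS therapy is widely used inappropriately, which weakens the assumption that ICS/LABA choice tracks exacerbations. This stands too. Even so, the current plan gives no means of checking whether the shares are equal.

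**Conclusion.** The point holds as a gap in covariate definition. An exacerbation treated on the index date has no exacerbation or severity term. Its only route into the score is a diffuse antibiotics item whose window differs between SAP 7.3 and Table 1. An episode treated with an oral corticosteroid alone leaves no trace. The score, the standardized-difference check and the conditional regression adjustment cannot repair this, because the variable is never built.

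The size is unknown. On the assumed inputs the factor on the hazard ratio is about 0.98 to 0.88 at time zero. It is nearer 1 when follow-up is averaged, when antibiotics capture some episodes or when the raised hazard is short-lived, and exactly 1 when the shares are equal. A reader might infer from the 0.917 scenario that bias could account for most of the planned effect of 0.90. That is one selected scenario on figures the documents do not contain, and it should not be reported as an expected bias.

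The outcome wording also needs settling. SAP 7.2.1 counts events after the index date and SAP 10.1 follows patients from it, so an index-day episode is either unassigned or a day-zero event. The change is worth making because it is cheap and uses claims already held, not because bias has been shown.

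**What to change.** In SAP 7.3 and Protocol 9.3.3:

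1. Add a separate index-date exacerbation covariate. It would be positive for either of these dated on the index date: a COPD outpatient visit with an oral corticosteroid or respiratory antibiotic, or an emergency visit or admission with a primary COPD diagnosis. Enter it in the propensity score and give it its own row in Table 1.
2. Leave the drug-based severity categories (mild and moderate) ending before the index date, so that the index inhaler cannot define severity.
3. Align the Table 1 medication-history label with SAP 7.3.
4. State that primary-outcome counting starts the day after the index date, reconciling SAP 7.2.1 with SAP 10.1.
5. Add a sensitivity analysis that excludes patients with an index-date exacerbation.

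The cost is wording in both documents, one derived variable and one extra model run. The downside is small: same-day claims cannot be ordered against the dispensing, so a few events that followed it may be counted as baseline. The sensitivity analysis checks whether that matters.
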